## 9.2 Laboratory Assessments

Laboratory data for hematology and serum chemistry tests will be reported in International Units. Individual values outside the central laboratory reference ranges will be identified (by “H” for high and “L” for low) in the data listings displaying the absolute values for each patient.

### 9.2.1 Variables

The following Hematology, Chemistries, Urinalysis laboratory evaluations will be performed:

Panel name	Laboratory parameters included
Hematology	leukocytes, erythrocytes, hemoglobin, hematocrit, thrombocytes (platelets); differential white blood cell count (neutrophils, lymphocytes, monocytes, basophils, eosinophils)
Chemistries	
- Enzymes	AST/SGOT, ALT/SGPT, gamma-GT, alkaline phosphatase, LDH
- Substrates	total protein, total bilirubin, creatinine, urea, uric acid
- Electrolytes	sodium, potassium, calcium
Urinalysis	glucose*, protein*, microalbumin**
Hormones	luteinizing hormone (LH), follicle stimulating hormone (FSH)
Pregnancy test	$\beta$ -HCG (in serum; for women of childbearing potential only)

\* In case there is no possibility for evaluation of the parameters provided above semiquantitative dipstick analysis will be accepted.

\*\* In cases where 24-hour urine is not available to determine microalbumin, the microalbumin/creatinine ratio may be used instead.

### 9.2.2 Statistical Analysis

Continuous laboratory test results will be summarized descriptively by study drug received for actual values and for changes from baseline. Visits to be summarized include all scheduled post-Cycle 1 Day 1 visits. Unscheduled visit data is not captured in summary statistics.

Shift from baseline tables for laboratory parameters will be presented. Categories will be based on CTCAE grade (where applicable) or by high/low flags (where CTCAE grades are not defined). Data will be analyzed at all post-Cycle 1 Day 1 visits, by worst grade post-Cycle 1 Day 1. Laboratory tests that have high and low abnormalities will be summarized separately for each direction (e.g., hypocalcemia and hypercalcemia). Worst post-baseline

values also include unscheduled visits. For WBC, neutrophils (absolute value) and thrombocytes extra shift table only considering cycle 1 lab results will be made in addition.

Abnormalities in laboratory tests that the investigator considered clinically significant (relevant) were to be recorded and summarized as AEs.

### **9.3 Vital Signs**

#### **9.3.1 Variables**

The following vital signs will be summarized:

- Blood pressure (systolic and diastolic, mmHg)
- Oral temperature (Celsius)
- Pulse rate (beats/min)
- Respiration rate (breaths/min)
- Body weight (kg)

#### **9.3.2 Statistical Analysis**

Summary tables of vital signs and change from baseline will be presented for all scheduled visits where vital signs were assessed. All recorded vital sign data will be listed.

### **9.4 Physical Examination**

Physical examination data will be presented in a data listing.

### **9.5 Cardiac Assessments**

#### **9.5.1 Left Ventricular Ejection Fraction (LVEF)**

LVEF (ECHO or MUGA) data (raw values and change from baseline) will be summarized descriptively (arithmetic mean, standard deviation, median, range interquartile values) by treatment at all available timepoints. In case only a range is specified for an LVEF measurement: use the mid-point (arithmetic mean) of the specified range as the substitute for the not-available point-value when calculating “Raw value result” and “Change”.

Moreover, a shift table will be made analyzing the data at all scheduled post-Cycle 1 Day 1 visits, by worst value post Cycle 1 Day 1 until end of study treatment (EOT) visit, and until end of post therapy follow-up. The following categories will be considered: FROM (%) 50-55, 55-60, 60-65, 65-70, 70-75 and >75 to <35, 40-35, 45-40, 50-55, 55-60, 60-65, 65-70, 70-75, >75. For LVEF-values specified by range the mid-point of the range should be used for the assignment. In addition, at the end of C3, C6, C7, C8, end of treatment and at post-therapy follow-up, number of subjects (and percentage) with absolute decline from baseline of 10% or more or absolute value of LVEF <50%, will be presented. Moreover, cumulatively at any time after C1D1, the following will be assessed: (number of subjects and percentage of):

- Absolute decline by 10% or more,
- Absolute decline by 15% or more,

- Absolute value of LVEF <50,
- Absolute value of LVEF <45%,
- Absolute decline from baseline of 10% or more or absolute value of LVEF <50%,
- Absolute decline from baseline of 15% or more or absolute value of LVEF <45%

A plot with mean LVEF (mean of raw LVEFE values) evolution over time –by treatment arm (including indication of number of patients present at each time point) will also be made.

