- 6) Patients discontinuing study treatment for reasons other than disease progression will be reassessed at 3-month intervals to assess the time to treatment failure (progression / death). Follow-up until progression will be suspended in patients in whom a new cancer treatment has been started without prior documentation of progressive disease. Information on survival status may be captured by telephone if no follow-up visit is scheduled for other reasons.
- 7) If treatment was discontinued because of a drug-related adverse event (i.e., causality at least possibly related), the patient will be followed up as clinically indicated to assess and document the outcome.
- 8) Only required in women of child-bearing potential
- 9) Only a patient developing signs of cardiac failure during post-treatment follow-up will have LVEF and ECG evaluated; a left ventricular dysfunction of CTCAE grade 4 will be reported as an SAE.
- 10) Only anticancer treatments that a patient received during post treatment follow-up for survival will be recorded.
- 11) For tests performed by a laboratory not affiliated to study site (e.g. mid-cycle controls by the patient's home doctor) copies of the external laboratory reports will be provided to the sponsor and results recorded in the CRF.
- 12) A PK sub-study, including electrocardiographic evaluations on Day 1 and Day 2, will be conducted at selected investigational sites. Procedures are described in [APPENDIX 7](#)
- 13) Every effort should be made to start treatment within 4 days of randomization.
- 14) Specimens from FFPE fresh biopsies if FFPE archival tumor specimens are not available.
- 15) Except for Day 1 clinical laboratory tests
- 16) Recommended to be conducted also at end of Cycle 7 and 8 (i.e., before start of Cycle 8 and Cycle 9, respectively) for both arms. Results are to be captured on the eCRF if there is an abnormal finding.
- 17) Sparse PK sampling of AEZS-108 treated patients will be performed at all investigational sites, where feasible. Sparse PK sampling is expected in Cycle 1 or alternatively in a subsequent cycle of ongoing patients, within the following time windows:
 - sample #1: within 60 minutes before end of the 2-hour infusion (during 2nd half of the infusion period);
 - sample #2: between 30 and 60 minutes after the end of infusion (EOI);
 - sample #3: between 120 and 180 minutes after EOI;
 - sample #4 (optional): between 4 and 6 hours after EOI.

TABLE OF CONTENTS

Protocol Authorization.....	2

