7.2.1.3 Documentation of routine safety parameters

A value outside the normal or reference range in a routine safety assessment, such as clinical laboratory, vital signs, or ECG, may signify an adverse finding. If the investigator considers the abnormality as clinically significant/relevant, as defined below, he should also record this on the CRF Adverse Events [Note: A clinically significant abnormality observed prior to first administration of study treatment should be recorded as update of the CRF Medical History]. If the findings contribute to a clinical diagnosis, such as hepatitis in case of increased liver enzymes, this diagnosis should be recorded as adverse event.

An abnormality must be considered as clinically significant, if

- it represents a serious adverse event, or
- it led to premature discontinuation of the study, or
- it required a therapeutic measure, or
- in the judgment of the investigator - it indicates a medically relevant condition or risk, without meeting any of the above criteria.

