8.4.4 Procedures during Cycle 2-9

Depending on hematological toxicities and any safety issues observed during Cycle 1, scheduling of hematological controls and/or other investigations is at the discretion of the investigators. For tests performed by a laboratory not affiliated with the study site (e.g. mid-cycle controls by the patient's home doctor) copies of the external laboratory reports will be provided to the sponsor and results reported in the CRF.

Adverse findings in such controls/investigations/diaries that the investigator considers as clinically important/significant will be recorded as Adverse Event.

8.4.5 Procedures at the end of Cycle 3 and 6

The following assessments will be performed at end of Cycle 3 and Cycle 6, i.e. together with the assessments required to assure continuation of study treatment with Cycle 4 and Cycle 7, respectively.

- **Cardiac function:**
 - Left ventricular ejection fraction (LVEF): echocardiogram or MUGA

Note: Recommended to be conducted also at end of Cycle 7 and 8 (i.e., before start of Cycle 8 and Cycle 9, respectively) for both arms. Results are to be captured on the eCRF if there is an abnormal finding.
- **Quality of Life:** questionnaires
- **Tumor imaging (CT or MRI):** evaluation of time-point response by comparison with target and non-target lesions defined at screening (baseline)

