8.6 Post-treatment follow-up

A patient developing signs of cardiac failure during post-treatment follow-up will have LVEF and ECG evaluated; a left ventricular dysfunction of CTCAE Grade 4 will be reported as an SAE.

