10.5 Documentation obligations

10.5.1 Data collection / electronic case report forms (eCRFs)

All trial data will be recorded on electronic CRFs (eCRF) supplied by the sponsor. Access to the eCRF will be restricted and password-controlled to the investigator and authorized co-workers according to the list of *Authorized Study Personnel*. Case report forms should be completed in English. Generic names for concomitant medications may be entered in the local language.

All data entries into eCRFs must be supported and verifiable from source documents to be retained in patient/hospital files.

Detailed guidance on the use of the eCRFs will be provided in a separate data entry training manual.

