APPENDIX 2: ECOG PERFORMANCE STATUS SCALE

Grade	Descriptions
0	Normal activity. Fully active, able to carry on all pre-disease performance without restriction.
1	Symptoms, but ambulatory. Restricted in physically strenuous activity, but ambulatory and able to carry out work of a light or sedentary nature (e.g., light housework, office work).
2	In bed <50 % of the time. Ambulatory and capable of all self-care, but unable to carry out any work activities. Up and about more than 50 % of waking hours.
3	In bed >50 % of the time. Capable of only limited self-care, confined to bed or chair more than 50 % of waking hours.
4	100 % bedridden. Completely disabled. Cannot carry on any self-care. Totally confined to bed or chair.
5	Dead.

**APPENDIX 3: GRADING OF LEFT VENTRICULAR FUNCTION
(CTCAE-V4.03)**

Adverse Event Category: Cardiac general

Adverse Event / Short Name: Left ventricular systolic dysfunction

Grade 1	Grade 2	Grade 3	Grade 4	Grade 5
-	-	Symptomatic due to drop in ejection fraction responsive to intervention	Refractory or poorly controlled heart failure due to drop in ejection fraction; intervention such as ventricular assist device, intravenous vasopressor support, or heart transplant indicated	Death

Adverse Event Category: Investigations

Adverse Event / Short Name: Ejection fraction (EF) decreased

Grade 1	Grade 2	Grade 3	Grade 4	Grade 5
-	Resting EF 50 – 40 %; 10 – 19 % drop from baseline	Resting EF 39 – 20 %; > 20 % drop from baseline	Resting EF < 20 %	Death

Source: CTCAE v4.03 publish date: June 14, 2010)

(see: http://evs.nci.nih.gov/ftp1/CTCAE/CTCAE_4.03_2010-06-14_QuickReference_5x7.pdf)

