- 4) Start of a new cycle is planned every 3 weeks unless treatment delay is required due to residual toxicity. Per footnote 1, a window of up to 3 days is allowed to schedule tests prior to the anticipated day of retreatment, to assure sufficient recovery from treatment-related adverse events ('toxicity') prior to dosing.
- 5) A full End-of-Therapy assessment will be also required whenever a patient is being withdrawn from the study. The reason(s) for discontinuation will be documented.
- 6) Patients discontinuing study treatment for reasons other than disease progression will be reassessed at 3-month intervals to assess the time to treatment failure (progression / death).
 

Follow-up until progression will be suspended in patients in whom a new cancer treatment has been started without prior documentation of progressive disease.

Information on survival status may be captured by telephone if no follow-up visit is scheduled for other reasons.
- 7) If treatment was discontinued because of a drug-related adverse event (i.e., causality at least possibly related), the patient will be followed up as clinically indicated to assess and document the outcome.
- 8) Only required in women of child-bearing potential
- 9) Only a patient developing signs of cardiac failure during post-treatment follow-up will have LVEF and ECG evaluated; a left ventricular dysfunction of CTCAE grade 4 will be reported as an SAE.
- 10) Only anticancer treatments that a patient received during post treatment follow-up for survival will be recorded.

- 11) For tests performed by a laboratory not affiliated to study site (e.g. mid-cycle controls by the patient's home doctor) copies of the external laboratory reports will be provided to the sponsor and results recorded in the CRF.
- 12) The pharmacokinetic sub-study will be conducted at selected investigational sites. Procedures are described in Appendix 7 of the protocol.
- 13) Every effort should be made to start treatment within 4 days of randomization.
- 14) Specimens from FFPE fresh biopsies if FFPE archival tumor specimens are not available.
- 15) Except for Day 1 clinical laboratory tests
- 16) Recommended to be conducted also at end of Cycle 7 and 8 (i.e., before start of Cycle 8 and Cycle 9, respectively) for both arms. Results are to be captured on the eCRF if there is an abnormal finding.

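### SAP 9.5.1 treats selectively tested and recorded LVEF (Cycles 7 and 8, post-therapy) as ordinary visit data, and its shift table has no category between 45 and 50

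*SAP*

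**What the plan says.** **Planned outputs.** SAP 9.5.1 asks for descriptive statistics of raw LVEF and change from baseline by treatment wherever data are available, and for a plot of mean LVEF over time showing patient numbers. It also asks, "at the end of C3, C6, C7, C8, end of treatment and at post-therapy follow-up, number of subjects (and percentage"), for patients with an absolute decline of 10% or more or a value below 50%. Counts at any time after Cycle 1 Day 1 follow. No denominator is given for any of these percentages.

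**What is collected.** Protocol 8.4.5 and footnote 16 of the protocol flow chart (repeated in SAP Appendix A) say of the later cycles: "Recommended to be conducted also at end of Cycle 7 and 8". The recording rule is "Results are to be captured on the eCRF if there is an abnormal finding". After treatment, protocol 8.6 says "A patient developing signs of cardiac failure during post-treatment follow-up will have LVEF and ECG evaluated", and footnote 9 of SAP Appendix A makes the restriction explicit: "Only a patient developing signs of cardiac failure during post-treatment follow-up will have LVEF and ECG evaluated".

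**Shift table.** The destination categories in SAP 9.5.1 are, in order: below 35, 40-35, 45-40, 50-55, 55-60, and so on to above 75.

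**The concern.** The SAP handles Cycles 7 and 8 like Cycles 3 and 6, although only the latter are required for every patient still on treatment. If sites follow the recording rule, a Cycle 7 or 8 value reaches the database because it is abnormal, so it is selected on the outcome being averaged. Follow-up values are selected indirectly, through cardiac signs. Patient numbers on the plot would show that few patients contribute, but not how they were chosen. SAP 9.2.2 keeps unscheduled laboratory results out of summary statistics; LVEF has no comparable rule.

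These late visits also carry the highest cumulative exposure. A control patient on the full planned dose has received 7 × 60 = 420 mg/m² by the end of Cycle 7 and 8 × 60 = 480 mg/m² by the end of Cycle 8, against the protocol's 550 mg/m² lifetime limit.

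The range missing from the shift table lies between the 50% eligibility limit (protocol 5.2, criterion 5) and the 45% cardiac-toxicity limit (protocol 5.3). The table could not directly show patients who moved into it.

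**Working it through.** The plan states no LVEF rate, mean or SD, so there is no figure to reproduce.

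**1. Shift categories.** Every value from 20 to 90 in steps of 0.5 was assigned to the listed destination bands, endpoints included.
- 45.5 to 49.5: no category.
- 40, 55, 60, 65 and 70: two categories each.
- 45 and 50: one category each.

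**2. Denominator.** Assume 75 of 250 patients in an arm reach Cycle 7 and 10% of those are abnormal, i.e. 0.10 × 75 = 7.5 expected patients. The same patients read as:
- 7.5/250 = 3% of the arm;
- 7.5/75 = 10% of those at the visit;
- 100% of those recorded, if only abnormal results are entered.

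**3. Effect of selective recording.** Let p be the true abnormal share, q the share of normal results that sites also enter, and m_A and m_N the mean LVEF in abnormal and normal patients.
- Recorded mean = [p·m_A + q(1−p)·m_N] / [p + q(1−p)].
- Abnormal share among recorded = p / [p + q(1−p)].

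Worked cases (assumed): baseline mean 62, SD 6, truncated at 50; abnormal = below 50 or a fall of 10 points or more.

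| Change, mean (SD) | True mean | Recorded mean, q=0 | Recorded mean, q=0.5 | True abnormal | Abnormal among recorded, q=0.5 |
|---|---|---|---|---|---|
| -2 (5) | 60.3 | 48.9 | 59.2 | 11.2% | 20.1% |
| -3 (5) | 59.3 | 48.9 | 58.0 | 14.8% | 25.8% |
| -4 (6) | 58.3 | 48.6 | 56.5 | 22.8% | 37.1% |

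First row, last column: 0.112 / (0.112 + 0.5 × 0.888) = 0.112 / 0.556 = 20.1%.

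**4. Wider range.** There were 21 scenarios: baseline mean 63, SD 6, at least 50; mean change -2, -4 or -6. Nine have independent changes (SD 5, 6 or 7). Twelve have follow-up correlated with baseline (r 0.5 or 0.7, SD 6 or 7). Points by which the Cycle 7/8 mean is too low:

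| q | Abnormal = below 50 | Abnormal = below 50 or fall ≥10 |
|---|---|---|
| 0 | 10.0-15.4 | 4.8-12.0 |
| 0.10 | 2.7-8.1 | 3.0-7.3 |
| 0.25 | 1.1-4.8 | 1.3-4.4 |
| 0.50 | 0.4-2.2 | 0.5-2.2 |

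- The true share meeting the SAP's by-visit criterion is 6-34%. Among recorded patients it reads 100% at q=0 and 9-51% at q=0.50; the 9% arises when only values below 50 count as abnormal.
- With no true arm difference, entry rates that differ by arm (q from 0 to 0.50) create an apparent difference of 0.7-13.9 points. A true 4-point difference then appears anywhere from -9.2 to 14.8.
- The band above 45 and below 50 holds 3-13% of all values.

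Post-therapy follow-up was not simulated.

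**5. Which falls are captured.** The recording rule does not define abnormal for LVEF. A fall of 15 points or more is a withdrawal reason in protocol 5.3, and protocol 7.2.1.3 treats an abnormality as clinically significant if "it led to premature discontinuation of the study", so such falls should be recorded. Falls of 10 to <15 points that end at 50 or above (3-14% of patients in the scenarios) are less clear. Protocol Appendix 3 grades "10 – 19 % drop from baseline" as Grade 2, but the recording rule does not refer to it.

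**The case against.** **Abnormal is not wholly undefined.** Protocol 7.2.1.1 uses CTCAE to grade abnormal findings, and Appendix 3 grades ejection fraction. On that reading, falls of 10 points or more are captured, the late-cycle counts among tested patients are nearly complete, and the smaller q=0 range (4.8-12.0) is the better supported. This is a fair reading, but that section concerns severity grading and does not set the recording rule. The means and denominator remain a problem either way.

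**Normal results may be entered.** Protocol 10.5.1 says "All trial data will be recorded on electronic CRFs (eCRF) supplied by the sponsor". This shrinks the bias without removing it, because entry of normal results is still not required at these visits.

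**The sizes are assumed.** That is true, and nothing in the documents indicates that entry differs by arm; the arm-difference figures show only what could happen. The model also ignores LVEF withdrawals before Cycle 7. Adding withdrawal at Cycle 6 to the independent-change scenarios (assumed correlation of changes 0.6) lowers the highest abnormal share from 34% to 27% and the highest share in the missing band from 12.6% to 10.7%. It barely moves the q=0 bias.

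**Denominators belong in table shells.** SAP section 9 names the safety population, and shells may say more. Taken alone, the missing denominator is only missing detail.

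**Protocol 9.6.3.3 wants LVEF summarised over the course of the study.** Cycle 3, Cycle 6 and end of treatment still meet that, and protocol section 9 allows the SAP to revise methods.

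**The consequence is limited.** SAP section 9 calls formal safety comparisons post-hoc. Cycle 3, Cycle 6 and end-of-treatment values are unaffected, and worst-value and any-time counts largely so. The missing band can be recovered overall as N(<50) minus N(<45), by baseline category from row totals if shown, or from Listing 16.2.8.5. All of this stands and limits the importance of the point.

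**Conclusion.** The concern holds; the change should be made. Both defects are in the text: selectively obtained LVEF goes into unrestricted means and percentages, and the shift table cannot place values above 45 and below 50. The downward direction of the Cycle 7/8 bias follows from preferential recording of low values. Its size depends on assumed LVEF distributions and entry rates: 4.8 to 15.4 points if no normal results are entered, and 0.4 to 2.2 if half are. The effect on the arm difference cannot be predicted, because testing is optional and the trial is open-label. What is at stake is the presentation of cardiac safety, not a hypothesis test.

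**What to change.** In SAP 9.5.1 and the table shells:

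- Remove Cycle 7, Cycle 8 and post-therapy follow-up from the mean and change summaries, the mean plot and the by-visit percentages.
- Report abnormal findings at those timepoints as counts beside the number of patients who reached the visit. Add a note that testing and capture were selective, so a patient without a recorded abnormality was not necessarily tested.
- State the denominator for the remaining by-visit percentages.
- Base the between-arm description on Cycle 3, Cycle 6, end of treatment and the any-time counts.
- Use non-overlapping shift bands on both axes (<35, 35-<40, 40-<45, 45-<50, 50-<55, and so on to 75 or more) and show row totals.

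This needs no protocol change, new data or site work. The cost is fewer by-visit outputs at late cycles.

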### 9.5.2 Electrocardiogram (ECG)

For all 12-ECGs recorded as part of the core study, the global classification of clinically significant (relevant) abnormalities will be summarized. For all continuous ECG variables, descriptive statistics (arithmetic mean, standard deviation, median, range interquartile values) will be used for summaries of all continuous ECG variables and their changes from baseline.

Categorical analysis will be performed (by means of frequency tables, worst post-cycle 1 day 1 until post-therapy FU result) with respect to QTcF and other cardiac intervals for the following categories:

*Absolute values:*

- $QTc \leq 450$  ms
- $QTc > 450$  ms and  $\leq 480$  ms
- $QTc > 480$  ms and  $\leq 500$  ms
- $QTc > 500$  ms
- $PR > 220$  ms
- $QRS > 110$  ms

*Change from baseline in cardiac intervals:*

- $\Delta QTc$  increase  $\leq 30$  ms
- $\Delta QTc$  increase  $> 30$  ms and  $\leq 60$  ms
- $\Delta QTc$  increase  $> 60$  ms
- $\Delta PR > 25\%$
- $\Delta QRS > 25\%$

The heart rate corrected QTc interval will be calculated according to

Bazett's formula ( $QTcB = \frac{QT}{\sqrt{RR}}$ ),

or Fridericia's formula ( $QTcF = \frac{QT}{\sqrt[3]{RR}}$ ),

where QTc is the QT interval corrected for rate, and RR is the interval from the onset of one QRS complex to the onset of the next QRS complex, measured in milliseconds.

RR interval (sec) = 60 / HR; with Heart Rate (HR) in beats per minute.

For patients participating in the PK sub-study, descriptive analyses of results and changes from baseline will be performed. More details can be found in the SAP supplement for the PK/QTc sub-study.

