7.2.3.1 ECG

The ECG will be recorded as scheduled in the flow-chart by means of a 12-lead (I, II, III, aVR, aVL, aVF, V₁-V₆) ECG system over a duration of 10 sec while the subjects will rest in supine position. The chart speed will be set at 25 mm/sec. The ECG patterns will be analyzed qualitatively with particular emphasis on changes in the T-wave duration and

morphology. The following will be computed by the ECG machine: heart rate, time intervals such as PQ/PR, QRS and QT interval, the heart rate corrected QTc interval calculated according to Bazett's formula ($QTcB = QT/\sqrt{RR}$) or Fridericia's formula ($QTcF = QT/\sqrt[3]{RR}$), where QTc is the QT interval corrected for rate, and RR is the interval from the onset of one QRS complex to the onset of the next QRS complex, measured in seconds.

The investigator should comment on the CRF on any deviation from normal that is considered clinically significant/relevant. If a finding is considered as clinically significant as defined in above, in [Section 7.2.1.3](#), it must also be documented on the CRF Adverse Events.

For recording and evaluation of ECGs within the pharmacokinetic sub-study, refer to [Appendix 7](#) of the protocol.

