In 5.1. Disposition: correct typo in country abbreviations per territory

In 6.1. Prior In 6.1. Treatment for Endometrial Cancer: remove ITT and explain how to analyze

In 6.2. Prior and Concomitant Medications: explain how to analyze

In 6.3. Study treatment exposure: addition of summaries will be made on patients receiving prophylactic antiemetic treatment per treatment cycle, and patients receiving anti-allergic treatment per treatment cycle

Efficacy analysis:

For backward selection in multivariate Cox model and logistic regression model: the significance level to retain a variable in the model will be set at 10%

Sensitivity analysis for ORR: logistic regression models will be used. For ORR, in addition: duration of overall response, duration of stable disease and duration of follow-up will be analyzed

PFS will be analyzed in the subset of patients from MITT that have CR, PR or SD as best overall response

Slight adaptation in description for mixed model approach for analysis of questionnaires

Adverse event analysis:

Clarification of time on treatment (date of last dose before AE onset – C1D1) and time since last dose (start date of AE – date of last dose before AE onset).

Addition: If treatment-relatedness is missing, AE will be considered as RELATED.

Extra AE tables by PT only ( $\geq$  certain cut-off)

Addition of tables for serious TEAEs grade 3/4 and 5

ECG: update of formulas for calculation of QTcB and QTcF

Addition of Appendix E: list of TLFs

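### SAP 9.5.2 gives the RR interval in the QTc formulas two different units; the millisecond wording contradicts the SAP's own next line and the protocol, and would make QTcF ten times too small if it were programmed

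*SAP*

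**What the plan says.** SAP 9.5.2 covers the ECGs of the core study. It gives Bazett's formula as QT divided by the square root of RR and Fridericia's as QT divided by the cube root of RR. Neither contains a factor of 1000. The sentence that defines the terms says "RR is the interval from the onset of one QRS complex to the onset of the next QRS complex, measured in milliseconds".

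The line directly below it reads "RR interval (sec) = 60 / HR; with Heart Rate (HR) in beats per minute".

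Protocol 7.2.3.1 has the same two formulas and an almost identical sentence with the other unit: "RR is the interval from the onset of one QRS complex to the onset of the next QRS complex, measured in seconds".

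The protocol also says where the core-study values come from: "The following will be computed by the ECG machine: heart rate, time intervals such as PQ/PR, QRS and QT interval". The list goes on to include the rate-corrected QTc, by Bazett or by Fridericia.

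In the SAP the categorical analysis is specified "with respect to QTcF and other cardiac intervals for the following categories". The absolute classes are ≤ 450, > 450 to 480, > 480 to 500 and > 500 ms. The change classes are increases of ≤ 30, > 30 to 60 and > 60 ms. SAP Appendix E lists the resulting outputs as Table 14.3.4.17 (ECG summaries) and Table 14.3.4.18 (ECG categorical analysis).

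**The concern.** The SAP is the specification from which the tables are programmed, and here two adjacent lines give different units for the same quantity. The unit matters because both formulas divide by a root of RR. With QT in milliseconds, they return a QTc on the scale of the 450, 480 and 500 ms cut-offs only when RR is in seconds.

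At stake are the core-study QTc tables, in a trial that compares a doxorubicin conjugate with doxorubicin. If the wrong unit were used and not noticed, the categorical table would show no QTc prolongation in either arm, whatever the data were.

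The SAP's document history for version 4 records "ECG: update of formulas for calculation of QTcB and QTcF". The formulas were therefore revisited in that version, and the current text still carries both units.

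**Working it through.** The documents give no worked QTc value, so there is no figure of the plan's own to reproduce. The check applies the stated formulas under each unit.

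**Inputs**
- Formulas: QTcB = QT/√RR and QTcF = QT/∛RR (SAP 9.5.2 and Protocol 7.2.3.1).
- RR in seconds = 60/HR (SAP 9.5.2); RR in milliseconds = 60,000/HR.
- Class limits: 450, 480 and 500 ms; changes of 30 and 60 ms (SAP 9.5.2).
- QT and heart-rate values are assumptions for illustration: QT 360 to 600 ms and HR 50 to 120 bpm.

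**Size of the discrepancy.** It does not depend on the patient. Moving RR from seconds to milliseconds multiplies it by 1000, so QTcF is divided by ∛1000 = 10.0 and QTcB by √1000 = 31.6.

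**Examples**

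| HR (bpm) | QT (ms) | QTcF, RR in s | QTcF, RR in ms | QTcB, RR in s | QTcB, RR in ms |
|---|---|---|---|---|---|
| 75 | 400 | 430.9 | 43.1 | 447.2 | 14.1 |
| 75 | 450 | 484.7 | 48.5 | 503.1 | 15.9 |
| 100 | 400 | 474.3 | 47.4 | 516.4 | 16.3 |
| 120 | 600 | 756.0 | 75.6 | 848.5 | 26.8 |

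For the first row, RR = 60/75 = 0.8 s = 800 ms. Then 400/∛0.8 = 430.9 and 400/∛800 = 43.1.

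**Absolute classes.** With RR in milliseconds, QTcF exceeds 450 only if QT exceeds 450 × ∛RR:
- at 120 bpm, 450 × ∛500 = 3,572 ms;
- at 50 bpm, 450 × ∛1200 = 4,782 ms.

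The largest QT considered here is 600 ms, so every patient would be in the ≤ 450 ms class.

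**Change classes.** A true QTcF increase of 60 ms would appear as 60/10 = 6 ms. To enter the class above 30 ms, the true increase would have to exceed 30 × 10 = 300 ms; for the class above 60 ms, 60 × 10 = 600 ms. Both classes would in practice be empty.

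**With RR in seconds.** The values in the seconds columns are on the scale of the SAP's cut-offs. The formulas are then correct as printed.

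**The case against.** The strongest reply is that the SAP's only instruction on how to obtain RR is the 60/HR line, and that line gives seconds. Protocol 7.2.3.1 names heart rate, PQ/PR, QRS, QT and QTc as machine output but does not name RR. A programmer would therefore probably derive RR from heart rate and get correct values. If the machine's own QTc is tabulated, the unit sentence has no effect at all. A mean QTcF near 43 ms in the summaries that the same section requires would also be hard to miss. These points stand, and they make the consequence conditional.

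They do not remove the contradiction. Nor does the machine's QTc settle the matter: the protocol allows it to be Bazett or Fridericia, the SAP's classes are specified on QTcF, and the SAP says that QTc will be calculated and supplies a rule for RR. The documents do not say which source feeds the tables.

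Three other limits are fair:
- The Bazett factor of about 32 does not bear on the classes as specified, because these are on QTcF.
- The PR and QRS thresholds are untouched.
- The PK sub-study is not shown to be affected. Protocol Appendix 7, section 8, has a core laboratory measure RR and QT with its own validated procedures, and SAP 9.5.2 refers that analysis to a separate supplement.

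**Conclusion.** The RR definition in SAP 9.5.2 is wrong as written for the formulas beside it, and it contradicts both the following line and Protocol 7.2.3.1. If that definition were programmed, QTcF would be 10 times too small, all patients would be classed ≤ 450 ms, and the classes for increases above 30 ms would in practice be empty. QTcB would be 31.6 times too small, in the continuous summaries only. The two factors are exact; the emptying of the classes rests on the assumed ranges of QT and heart rate, with a wide margin.

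A reader might infer that the SAP's formulas will put every patient in the lowest class. The documents do not support that, because the SAP also gives the correct derivation in seconds and the protocol has the ECG machine compute QTc. A reader might also infer that all core-study ECGs need central recomputation. That does not follow from a unit error: central evaluation is described only for the sub-study. The defect should be corrected, but it does not touch the primary endpoint.

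**What to change.** In SAP 9.5.2, replace milliseconds by seconds in the definition of RR, and say that QT is in milliseconds and RR in seconds. This agrees with the 60/HR line and with Protocol 7.2.3.1.

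Add one sentence stating whether the QTcF in Tables 14.3.4.17 and 14.3.4.18 is taken from the ECG machine or derived from QT and heart rate. If it is taken from the machine, the sentence should also cover ECGs for which only a Bazett value is available.

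The cost is one word and about one sentence in the SAP before database lock. No new data collection is needed.
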